### 3. STUDY DESIGN

[figure not shown]
#### 3.1. Study Overview

This is a randomized, double-blind, placebo-controlled, 5-arm (placebo, plus 4 active doses of PF-05221304), parallel-group study.

Determination of eligibility for this study will occur via a sequential, 3-step process – starting with pre-qualification. Subjects identified to be eligible based on pre-qualification will then undergo Visit 1 (Screen 1) with only those confirmed to continue to be eligible progressing to Visit 2 (Screen 2). For a given subject, this 3-step eligibility assessment (from pre-qualification to Screen 2, inclusive) may take up to 2-months.

Once confirmed to be eligible based on Screen 2 procedure(s), subjects will progress to a run-in phase when concomitant treatment(s) will be stabilized, and baseline-related visits will occur. At Visit 5 (Day 1), subjects will be randomized to receive 1 of 5 blinded regimens for a duration of up to 16 weeks (ie, 108±4 days). Excluding the pre-qualification visit, this study includes a total of 12 *scheduled* outpatient visits *in the morning*, CCI and a potential for up to at least 3 visits for repeat assessments (for procedures/tests at Visit 1, Visit 2, or 2nd Follow-up visit). The total participation, from Visit 1 (Screen 1) to 2nd Follow-up visit, will be 27-weeks (minimum) to 35-weeks (maximum) – refer to [Figure 2](#).

**Figure 2. C1171002 Study Design**

At least 360 subjects (72 per arm) will be randomized at approximately 120 sites to ensure a minimum of 300 subjects (60 per arm) complete the study. ***In each arm***,  $\geq 50\%$  of subjects randomized will be deemed to be eligible for 1st tier stratification of diagnosed/presumed NASH; with the remaining subjects per arm eligible for 1st tier stratification of NAFLD with likely minimal inflammation and fibrosis – refer to [Section 4.3](#).

Subjects who are noted to have non-evaluable baseline MRI-PDFF, as determined by the sponsor-identified central imaging vendor, may be replaced, at sponsor discretion – refer to [Section 7.1.4](#); otherwise, there are no plans to replace subjects who are prematurely withdrawn. To ensure that the required minimum number of subjects complete the study, the plan is to overenroll by approximate 20% to account for premature early withdrawal.

### 3.2. Stopping Rules for Dosing in Individual Subjects

At investigator discretion, ***for subjects' safety***, dosing with double-blinded investigational product (ie, post randomization), may be stopped in an individual subject – either temporarily **or** permanently. In such cases, any open TEAEs must be followed to resolution or until such time that the event is viewed to have stabilized – refer to [Section 8](#) for details – specifically, [Section 8.1](#) which outlines the requirements for reporting adverse events, [Section 8.2.3](#) detailing definition of serious adverse events, and [Section 8.4.2](#) summarizing management of potential cases of drug-induced liver injury which are categorized as potentially important medical events.

An example where **temporary discontinuation of dosing** with investigational product, may be considered appropriate includes hospitalization with subsequent discharge within  $\leq 7$ -days in stable medical condition, as determined by medically-qualified investigator. Of note, in this study, re-challenge/re-initiation of dosing with double-blinded investigational product should **not** be attempted in subjects who meet threshold for withdrawal based on platelet count ([Appendix 2](#)) *or* fasting serum triglycerides ([Appendix 3](#)).

Examples where **permanent discontinuation of dosing** and withdrawal of the subject from the study is deemed appropriate, as determined by investigators' medical judgment, include:

- Hospitalization due to serious adverse event (SAE) resulting in clinical decompensation of the subject *and* necessitating continued inpatient stay for more than 7-days;
- Subjects observed to have a decline over time ultimately reaching the threshold of  $< 75,000/\text{mm}^3$  in platelet count – refer to [Section 7.9.1](#) and [Appendix 2](#) for additional guidance;
- Individual subjects with consistently increasing fasting serum triglycerides over time ultimately reaching the threshold of  $\geq 800$  mg/dL (9 mmol/L) – refer to [Section 7.9.2](#) and [Appendix 3](#) for additional guidance;
- Of note, in both the above cases of pre-identified laboratory thresholds, 1 additional unplanned assessment may be warranted *before* permanent withdrawal if the threshold is observed to be met as an isolated occurrence relative to all prior results *and* subject is asymptomatic.

### 3.3. Considerations for Pausing or Stopping Active Dose(s) Based on Observed Safety

The decision to pause *or* stop dosing at a study-level, for 1 or more active dose(s) of PF-05221304 may be considered based on recommendation from the Internal Review Committee (IRC) according to their review of unblinded, study-level emerging, *observed* safety data – refer to [Section 9.5](#).

***In addition***, during study conduct, after approximately ***every*** 20% of the total planned randomizations [for example: 72 subjects (20%), 145 subjects (40%), 215 subjects (60%), and 290 subjects (81%) of planned 360 subjects], based on blinded safety review by the selected members of the Sponsor's study team, unblinded review of the safety data by the IRC will be triggered and a determination of the safety to continue the study documented if post randomization ***either*** of the below conditions are met –

- More than 20% of subjects, develop a moderate or severe AE in the same system organ class (SOC);
- More than 15 % of subjects meet the individual permanent discontinuation of dosing rules ([Section 3.2](#)).

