#### 1.4. Summary of Benefit Risk Assessment

Study C1171002 is the first time that PF-05221304 is being administered to patients with NAFLD. For the subjects participating in this study, close monitoring of their medical condition and safety, will occur as outlined in this protocol. Those randomized to PF-05221304 may potentially derive benefit from reduction of DNL and its potential associated effects including reduction in hepatic steatosis, and potential reduction in liver inflammation. Those randomized to placebo are not expected to obtain any specific benefit, beyond close monitoring of their medical condition and safety. As of the issuance of this protocol, identified adverse drug reactions that may be encountered with the administration of PF-05221304 include elevation in blood triglycerides and reduction of platelet count.

Any adverse clinical impact of these findings are expected to depend on the severity of the potential reaction, and are minimized through – (1) the proposed frequent visits to site to permit close oversight of subjects’ safety via monitoring of a range of clinical assessments including laboratory tests, 12-lead ECGs, vitals, assessment of AEs; (2) inclusion of provisions for temporary discontinuation of dosing and permanent withdrawal from the study as outlined in [Section 3.2](#); (3) institution of an Independent Review Committee (IRC) to undertake unblinded review of the safety data, while the study is on-going, and make recommendation(s) as to whether 1 or more doses should be paused/discontinued (refer to [Section 3.3](#) and [Section 9.5](#)), amongst the planned activities.

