#### **7.9.3.1.3. Management of Hyperglycemia**

Hyperglycemia is defined as a glucose reading of  $> 270$  mg/dL (15 mmol/L) using sponsor-provided, plasma-referenced, home glucometers (or sponsor-identified central laboratory).

Subjects noted to have a **fasting** plasma glucose value (during home glucose monitoring using sponsor-provided, plasma-referenced, home glucometers **or** as reported by the sponsor-identified central laboratory) meeting the above definition of hyperglycemia must be instructed to repeat the measurement the next day (following  $\geq 8$ -hour fast except water). If the second measurement also meets the above definition, subjects must be asked to return to the site in the next  $5 \pm 2$  days, following  $\geq 8$ -hour fast except water, and have blood collected for fasting plasma glucose (and shipped to sponsor-identified central laboratory for analysis).

**If** the results from the sponsor-identified central laboratory confirm the readings using sponsor-provided, plasma-referenced, home glucometers **or** a previous result reported by the sponsor-identified central laboratory, the subject must be withdrawn from the study – with the reason for withdrawal captured as an adverse event of hyperglycemia.

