### **8.2.2. Abnormal Test Findings**

Abnormal objective test findings should be recorded as AEs when any of the following conditions are met:

- Test result is associated with accompanying symptoms; and/or

- Test result requires additional diagnostic testing or medical/surgical intervention; and/or
- Test result leads to a change in study dosing (outside of any protocol-specified dose adjustments) or discontinuation from the study, significant additional concomitant drug treatment, or other therapy; and/or
- Test result is considered to be an AE by the investigator or sponsor.

Merely repeating an abnormal test, in the absence of any of the above conditions, does not constitute an AE. Any abnormal test result that is determined to be an error does not require recording as an AE.

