### 8.3. Severity Assessment

If required on the AE page of the CRF, the investigator will use the adjectives MILD, MODERATE, or SEVERE to describe the maximum intensity of the AE. For purposes of consistency, these intensity grades are defined as follows:	
MILD	Does not interfere with subject's usual function.
MODERATE	Interferes to some extent with subject's usual function.
SEVERE	Interferes significantly with subject's usual function.

Note the distinction between the severity and the seriousness of an AE. A severe event is not necessarily an SAE. For example, a headache may be severe (interferes significantly with the subject's usual function) but would not be classified as serious unless it met one of the criteria for SAEs, listed above.

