3.4.2 Laboratory Data

For the specific laboratory parameters listed in Table 2 below, the following endpoints will be evaluated using CaPS:

- Absolute value and change from baseline at week 2, week 4, week 6, week 8, week 12, week 16, and Follow-up.
- Number of occurrences of these abnormalities defined as “Flag Level” or “Alert Level”
- Number of subjects with these abnormalities defined as “Flag Level” or “Alert Level”

Parameter	Flag Level	Alert Level	Conventional Units
Fasting Serum Triglycerides	≥ 400	≥ 600	mg/dL
	--	≥ 800	mg/dL
Platelet Count	< 100	< 75	$x 10^3$ /mm³
Fasting Plasma Glucose	< 70	≤ 49	mg/dL
	≥ 140	>270	mg/dL
Alanine aminotransferase	$\geq 2x$ ULN	Pfizer std flag for PCC	IU/L
Aspartate aminotransferase	$\geq 2x$ ULN	Pfizer std flag for PCC	IU/L

Alkaline Phosphatase	$\geq 2x$ ULN	Pfizer std flag for PCC	IU/L
Gamma Glutamyl Transferase	$> ULN$	Pfizer std flag for PCC	IU/L
Total Bilirubin	$> 1.5x$ ULN	Pfizer std flag for PCC	mg/dL
Direct (Conjugated) Bilirubin	$> ULN$	Pfizer std flag for PCC	mg/dL

*All flag level changes are cumulative from baseline (defined as result closest prior to dosing at Visit 5 (Day 1)); reflect either threshold for entry criteria into study or clinically significant thresholds

^All alert changes are cumulative from baseline (defined as result closest prior to dosing at Visit 5 (Day 1); values when noted during the study, by central laboratory necessitates rapid notification (via fax/e-mail) to site and Study Clinician

PCC – potential clinical concern

ULN – upper limit of normal as determined by the central laboratory

The safety events of special clinical concern as defined in Table 2 will be summarized and the frequency of laboratory abnormalities (both number of occurrence **and** number of subjects).

Across all the laboratory-related analytes (for safety and pharmacodynamics/biomarker), inclusion of results when assessed at scheduled nominal visits meet the following criteria:-

1. Collection must be prior to AM dose of double-blinded study medication
2. Collection permitted to be *nonfasted for the following analytes and will be permitted to be grouped with fasted results* given that nonfasted state is not known to impact results

Chemistry panel	Hematology	Other	Urinalysis
Total bilirubin	Hemoglobin	aPTT	pH

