7.2 Interim Analyses and Summaries

For planned interim analysis and for triggered unblinded reviews, IRC members will receive the following data summarized/analyzed by randomized arm along with the relevant subject data listings.

Study conduct and subject characteristics:

- Study conduct issues (e.g., enrollment status, currentness of the database, time between randomization and first treatment, eligibility violations)
- Subject evaluation groups
- Subject stratification factors
- Demographic and other baseline characteristics

Safety Data:

The Committee will monitor certain specific safety-related laboratory parameters, vital sign parameters, and treatment-emergent adverse events (TEAEs) as well as serious adverse events (SAEs including death) listings in an unblinded manner for overall

frequency of occurrence of events. To do so, here are the listings which should be provided:

- TEAEs (and SAEs) leading to temporary discontinuation of dosing in subjects;
- TEAEs (and SAEs) leading to permanent discontinuation and withdrawal of subjects;
- The listing of individual subject-level TEAEs and SAEs;
- All instances of hypoglycemia, or hyperglycemia, or platelet reduction, or hypertriglyceridemia leading to permanent withdrawal;
- Listing of Treatment emergent adverse events (TEAEs) under the 3-tier approach as defined in section 6.6 of this SAP;
- Listings of SAEs/deaths and narratives requested from the safety database (ie, ARGUS or similar)

CCI [REDACTED] laboratory parameters outlined in Table 2 of this SAP represent the minimum list of parameters which will be listed and provided to the committee. This list may be expanded depending on team blinded review.

The Committee will receive the distribution of subjects over time whose values cross the boundaries (ie Flag and Alert levels separately) for each of the parameters included in Table 2 of this SAP.

Percent change from baseline in other fasting lipid parameters including total cholesterol, direct low density lipoprotein cholesterol (LDL-C), very low density lipoprotein (VLDL) and high density lipoprotein cholesterol (HDL-C) will be also provided for review.

The following graphical representations of the parameters in Table 2, CCI [REDACTED] other fasting lipid parameters (see list above) will be provided:

- Individual values: median response with Q1 and Q3 per randomized arm over time, Box and whiskers plots as depicted in Appendix 3.2,

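### The rules that convene the IRC miss platelet and triglyceride changes short of the withdrawal thresholds unless these are graded moderate or severe AEs, and leave it unclear whether hyperglycemia withdrawals count

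*Protocol*

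**What the plan says.** Protocol 1.4 says that "identified adverse drug reactions that may be encountered with the administration of PF-05221304 include elevation in blood triglycerides and reduction of platelet count", and lists unblinded IRC review among the measures that limit their impact. Protocol 9.6 rules out a data monitoring committee, so the IRC is the only unblinded safety body described.

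Protocol 3.3, repeated in SAP 7.1, sets two conditions under which the blinded looks lead to an unblinded IRC review:
- Trigger 1, on adverse events: "More than 20% of subjects, develop a moderate or severe AE in the same system organ class (SOC").
- Trigger 2, on discontinuations: more than 15% "of subjects meet the individual permanent discontinuation of dosing rules", with a reference to section 3.2.

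Section 3.2 gives examples of permanent discontinuation: an SAE hospitalization with decompensation lasting beyond 7 days, a platelet decline to below 75,000/mm3, and a rise in fasting triglycerides to 800 mg/dL or more. The two laboratory rules do not require symptoms.

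On recording and grading, Protocol 8.2.2 lists when an abnormal test becomes an AE and adds that "Merely repeating an abnormal test, in the absence of any of the above conditions, does not constitute an AE". Under Protocol 8.3 an event is mild if it "Does not interfere with subject's usual function".

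SAP Table 2 (section 3.4.2) flags platelets below 100,000/mm3 and alerts below 75,000. It flags fasting triglycerides from 400 mg/dL and alerts from 600 and from 800. The footnote on Alerts reads "values when noted during the study, by central laboratory necessitates rapid notification", addressed to the site and the Study Clinician.

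Protocol 5.9 and 7.9.3.1.3 require withdrawal for confirmed hyperglycemia, "with the reason for withdrawal captured as an adverse event of hyperglycemia". SAP 7.2 lists among the IRC's data "All instances of hypoglycemia, or hyperglycemia, or platelet reduction, or hypertriglyceridemia leading to permanent withdrawal".

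**The concern.** The IRC is offered as mitigation for two laboratory effects that were described as asymptomatic in Phase 1. The rules that convene it are built on functionally graded AEs and on individual withdrawals. A laboratory shift can be widespread and dose-related without being either.

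The exposure is plausible. In Phase 1, triglycerides rose at 40 mg/day and above, and the top dose here is 50 mg. Platelets fell at 60 mg/day and above and not up to 40 mg/day, so 50 mg lies between the two. Phase 1 dosing lasted up to 14 days, against 16 weeks here, and Protocol 1.3.1 itself expects that exposure and response may vary more in outpatients.

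At stake is whether a spreading platelet or triglyceride effect would be examined by dose while the trial is running, at times other than the planned interim analysis. A smaller matter is whether a mandatory safety withdrawal can be left out of the withdrawal count.

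**Working it through.** **Inputs.** Looks at 72, 145, 215 and 290 of 360 randomized; limits of more than 20% and more than 15% (Protocol 3.3); 1:1:1:1:1 allocation (Protocol 4.3). The denominator is not defined. All subjects randomized to date is assumed.

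**1. The plan's own percentages.** 72/360 = 20.0%, 145/360 = 40.3%, 215/360 = 59.7%, 290/360 = 80.6%. These round to the stated 20, 40, 60 and 81%.

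**2. Smallest counts that fire each trigger** (smallest integer strictly above the limit).

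| Look | 0.20 × n | Trigger 1 | 0.15 × n | Trigger 2 |
|---|---|---|---|---|
| 72 | 14.4 | 15 | 10.8 | 11 |
| 145 | 29.0 | 30 | 21.75 | 22 |
| 215 | 43.0 | 44 | 32.25 | 33 |
| 290 | 58.0 | 59 | 43.5 | 44 |

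**3. What each laboratory level contributes.**

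| Finding, asymptomatic | Status in the documents | Trigger 1 | Trigger 2 |
|---|---|---|---|
| Platelets <75,000/mm3 | Section 3.2 rule; Table 2 Alert | Only if graded moderate or severe | Counts |
| Platelets 75,000 to <100,000 | Thrombocytopenia by Protocol 7.9.1; Table 2 Flag | Only if graded moderate or severe | Does not count |
| Triglycerides ≥800 mg/dL | Section 3.2 rule; Table 2 Alert | Only if graded moderate or severe | Counts |
| Triglycerides 600 to <800 | Table 2 Alert | Only if graded moderate or severe | Does not count |

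**4. Consequences.**
- Any number of subjects in the second or fourth row, graded mild or not recorded as AEs, add 0 to both triggers. The limiting case is 72 of 72 subjects with both counts at 0.
- If every active-arm subject fell below 75,000/mm3, the share would be 4/5 = 80%, above 15%, and Trigger 2 would fire.
- If one whole arm fell below 75,000/mm3, the share would be 1/5 = 20%, above 15%, and Trigger 2 would fire.
- For the second and fourth rows the outcome depends on grading. Let f be the share of subjects affected and g the share of those recorded as moderate or severe AEs in one organ class, with no other AEs in that class. Trigger 1 needs f × g > 0.20, so f > 0.20/g. The documents give no value for g. Over an assumed range, g = 1 needs f > 20%, g = 0.5 needs f > 40%, and at g = 0.2 or below the trigger cannot fire even with everyone affected.

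**5. Hyperglycemia withdrawals.** Take 11 such withdrawals among 72 subjects and no other discontinuations. If Trigger 2 counts only the items named in section 3.2, the result is 0/72 = 0%. If it counts every protocol-mandated safety withdrawal, the result is 11/72 = 15.3%, and it fires. The text does not settle which reading applies.

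**The case against.** A reader might infer that the triggers ignore the drug's identified harms altogether, so that thrombocytopenia could become universal unseen. The documents do not support that. Two of the three examples in section 3.2 are those harms, without any need for symptoms, and step 4 shows that counts below 75,000/mm3 in a single whole arm would fire Trigger 2. The statement holds only for changes that stay short of withdrawal and are graded mild or not recorded.

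Nor are asymptomatic laboratory findings barred from Trigger 1. Protocol 8.2.2 makes a result an AE if it requires further diagnostic testing, or if the investigator or sponsor considers it one. Platelets below the lower limit of normal at Week 8 already prompt extra visits. The one Phase 1 platelet event, an asymptomatic fall to 114,000/mm3, was graded moderate. That stands, but it is hard to square with the functional definition in 8.3. It shows that counting would depend on individual grading at about 120 sites.

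A reader might also infer that hyperglycemia withdrawals and potential Hy's law cases can never count. That goes too far. The section 3.2 list is illustrative and the section cross-refers to 8.4.2. Hyperglycemia withdrawals are recorded as AEs and can reach Trigger 1 if graded moderate or severe. Hy's law cases are reported as SAEs. What remains is ambiguity about Trigger 2.

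The strongest counter-argument is that the IRC has another route to these data. Protocol 9.5 requires at least one interim analysis, with no trigger needed, and SAP 7.2 then gives the IRC the Flag and Alert crossings. Alerts also reach the Study Clinician quickly. This limits the gap but does not close it: one analysis is planned, after about 120 subjects reach Week 6, and more are allowed but not promised.

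Finally, universal involvement is a limiting case, not a forecast. Phase 1 saw no thrombocytopenia at any dose. The IRC charter and the Appendix 2 and 3 figures cannot be read and may contain further criteria.

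**Conclusion.** The concern holds in this limited form. Neither trigger has a laboratory criterion short of individual withdrawal. Platelets of 75,000 to <100,000/mm3 and triglycerides of 600 to <800 mg/dL, if asymptomatic and graded mild or unrecorded, contribute 0 to both triggers at any frequency. Outside the at-least-one interim analysis, no readable rule would then convene the IRC, although section 1.4 relies on it for these reactions. The data that SAP 7.2 sends to the IRC once it meets cannot cause it to meet.

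Whether Trigger 2 counts the mandatory hyperglycemia withdrawals is an unresolved ambiguity, not an explicit exclusion.

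The conclusion assumes that sites follow 8.3 as written and that the unreadable charter and appendix figures add no trigger. No rate of these findings at the trial doses is given, so the likelihood of a missed signal cannot be quantified. Confidence is moderate. The gap deserves correction because it concerns safety oversight and is cheap to close.

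**What to change.** 1. In Protocol 3.3 and SAP 7.1, have the existing blinded team also tally, at each existing look, the subjects with post-randomization SAP Table 2 crossings for platelets and fasting triglycerides. Let that tally convene the existing IRC at a level and percentage chosen by the sponsor and IRC and written into the charter. In choosing the triglyceride level, note that the Flag of ≥400 mg/dL sits at the entry limit of ≤400 mg/dL, so ordinary variation could inflate a tally based on it.
2. Reconcile Protocol 3.2, 3.3, 5.9, 7.9.3.1.3 and 8.4.2 so that Trigger 2 states which protocol-mandated safety withdrawals it counts, and define its denominator.

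No individual stopping threshold changes. The laboratory data are already collected and the Alerts already sent, and the tally can be made blinded. The cost is wording in the Protocol, SAP and charter, a short tabulation at each look, and an IRC that may be convened somewhat more often.
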